1.0 TRIAL SUMMARY

Abbreviated Title	Phase I trial of pembrolizumab with vorinostat and temozolomide for newly diagnosed glioblastoma
Trial Phase	Ib
Clinical Indication	Newly diagnosed glioblastoma
Trial Type	Open label
Type of control	Not applicable
Route of administration	Intravenous, Oral
Trial Blinding	Not applicable
Treatment Groups	1 Group
Number of trial subjects	32
Estimated enrollment period	24 months
Estimated duration of trial	36 months
Duration of Participation	24 months
Estimated average length of treatment per patient	15 months

[figure not shown]

2.0 TRIAL DESIGN

2.1 Trial Design

This is a standard 3+3 design and will include 2 cohorts: 1) dose escalation cohort, and 2) dose expansion cohort. Dose escalation will occur separately for concurrent radiotherapy part of treatment and maintenance part of treatment.

2.2 Trial Diagram

Dose Escalation Phase

Dose Escalation Schedule During Radiotherapy Phase					
Dose Level	Dose				
	Pembrolizumab Vorinostat				
Level -1	200 mg IV every 3 weeks	100 mg/day orally on days 1-5 every week during radiotherapy			
Level 1	200 mg IV every 3 weeks	200 mg/day orally on days 1-5 every week during radiotherapy			
Level 2	200 mg IV every 3 weeks	300 mg/day orally on days 1-5 every week during radiotherapy			
	Dose Escalation S	Schedule During Maintenance Phase			
Dose Level Dose					
	Pembrolizumab	Vorinostat			
Level -1	200 mg IV every 3 weeks	200 mg/day orally 1 week on 1 week off after radiotherapy			
Level 1	200 mg IV every 3 weeks	300 mg/day orally 1 week on 1 week off after radiotherapy			
Level 2	200 mg IV every 3 weeks	400 mg/day orally 1 week on 1 week off after radiotherapy			

Twenty patients will be treated with vorinostat at MTD (from dose escalation phase), pembrolizumab, temozolomide and radiation

3.0 OBJECTIVE(S) & HYPOTHESIS(ES)

3.1 Primary Objective(s) & Hypothesis(es)

(1) **Objective:** To evaluate the safety, tolerability, and to determine the maximum tolerated dose (MTD) of vorinostat given in combination with pembrolizumab, temozolomide, and radiotherapy in patients with newly diagnosed glioblastoma.

Hypothesis: Combination of pembrolizumab and vorinostat with radiotherapy and temozolomide will have acceptable safety and tolerability.

3.2 Secondary Objective(s) & Hypothesis(es)

(1) **Objective**: To evaluate the 12 months and 24 months survival rate in patients with newly diagnosed glioblastoma who are treated with pembrolizumab in combination with vorinostat and standard treatment with radiotherapy and temozolomide.

Hypothesis: Addition of pembrolizumab and vorinostat to standard treatment with radiotherapy and temozolomide will augment the survival.

3.3 Exploratory Objective

(1) **Objective:** To explore tissue biomarkers that may predict tumor response to pembrolizumab in combination with vorinostat and standard treatment with radiotherapy and temozolomide in patients with newly diagnosed glioblastoma.

4.0 BACKGROUND & RATIONALE

4.1 Background

Refer to the Investigator's Brochure (IB)/approved labeling for detailed background information on pembrolizumab and vorinostat.

4.1.1 Pharmaceutical and Therapeutic Background

The importance of intact immune surveillance in controlling outgrowth of neoplastic transformation has been known for decades. Accumulating evidence shows a correlation between tumor-infiltrating lymphocytes (TILs) in cancer tissue and favorable prognosis in various malignancies. In particular, the presence of CD8+ T-cells and the ratio of CD8+ effector T-cells / FoxP3+ regulatory T-cells seems to correlate with improved prognosis and long-term survival in many solid tumors.

The PD-1 receptor-ligand interaction is a major pathway hijacked by tumors to suppress immune control. The normal function of PD-1, expressed on the cell surface of activated T-cells under healthy conditions, is to down-modulate unwanted or excessive immune responses, including autoimmune reactions. PD-1 (encoded by the gene Pdcd1) is an Ig superfamily member related to CD28 and CTLA-4 which has been shown to negatively

regulate antigen receptor signaling upon engagement of its ligands (PD-L1 and/or PD-L2). The structure of murine PD-1 has been resolved. PD-1 and family members are type I transmembrane glycoproteins containing an Ig Variable-type (V-type) domain responsible for ligand binding and a cytoplasmic tail which is responsible for the binding of signaling molecules. The cytoplasmic tail of PD-1 contains 2 tyrosine-based signaling motifs, an immunoreceptor tyrosine-based inhibition motif (ITIM) and an immunoreceptor tyrosinebased switch motif (ITSM). Following T-cell stimulation, PD-1 recruits the tyrosine phosphatases SHP-1 and SHP-2 to the ITSM motif within its cytoplasmic tail, leading to the dephosphorylation of effector molecules such as CD3ζ, PKCθ and ZAP70 which are involved in the CD3 T-cell signaling cascade. The mechanism by which PD-1 down modulates T-cell responses is similar to, but distinct from that of CTLA-4 as both molecules regulate an overlapping set of signaling proteins. PD-1 was shown to be expressed on activated lymphocytes including peripheral CD4+ and CD8+ T-cells, B-cells, T regs and Natural Killer cells. Expression has also been shown during thymic development on CD4-CD8- (double negative) T-cells as well as subsets of macrophages and dendritic cells. The ligands for PD-1 (PD-L1 and PD-L2) are constitutively expressed or can be induced in a variety of cell types, including non-hematopoietic tissues as well as in various tumors. Both ligands are type I transmembrane receptors containing both IgV- and IgC-like domains in the extracellular region and contain short cytoplasmic regions with no known signaling motifs. Binding of either PD-1 ligand to PD-1 inhibits T-cell activation triggered through the T-cell receptor. PD-L1 is expressed at low levels on various non-hematopoietic tissues, most notably on vascular endothelium, whereas PD-L2 protein is only detectably expressed on antigen-presenting cells found in lymphoid tissue or chronic inflammatory environments. PD-L2 is thought to control immune T-cell activation in lymphoid organs, whereas PD-L1 serves to dampen unwarranted T-cell function in peripheral tissues. Although healthy organs express little (if any) PD-L1, a variety of cancers were demonstrated to express abundant levels of this T-cell inhibitor. PD-1 has been suggested to regulate tumor-specific T-cell expansion in subjects with melanoma (MEL). This suggests that the PD-1/PD-L1 pathway plays a critical role in tumor immune evasion and should be considered as an attractive target for therapeutic intervention.

Pembrolizumab is a potent and highly selective humanized monoclonal antibody (mAb) of the IgG4/kappa isotype designed to directly block the interaction between PD-1 and its ligands, PD-L1 and PD-L2. KeytrudaTM (pembrolizumab) has recently been approved in the United Stated for the treatment of patients with unresectable or metastatic melanoma and disease progression following ipilumumab and, if BRAF V600 mutation positive, a BRAF inhibitor.

Temozolomide is an oral alkylating agent. Continuous daily temozolomide (75 mg per square meter of body-surface area per day, 7 days per week from the first to the last day of radiotherapy) plus radiotherapy (fractionated focal irradiation in daily fractions of 2 Gy given 5 days per week for 6 weeks, for a total of 60 Gy), followed by six cycles of adjuvant temozolomide (150 to 200 mg per square meter for 5 days during each 28-day cycle) is the United States Federal Drug Administration (FDA) approved treatment for patients with newly diagnosed glioblastoma [22]. This treatment increased the median survival from 12.1 months with radiotherapy alone to 14.6 months [22]. The side effects of treatment included:

grade 3 or 4 neutropenia in 4%, and grade 3 or 4 thrombocytopenia in 3%. The most common nonhematologic adverse event was moderate-to-severe fatigue [22].

Vorinostat is a small-molecule inhibitor of histone deacetylases (HDAC) that binds directly to the enzyme's active site in the presence of a zinc ion and is approved by the FDA for use in patients with advanced cutaneous T-cell lymphoma. Vorinostat crosses blood-brain barrier and has shown activity against high-grade glioma in preclinical studies [23]. As per vorinostat Investigator Brochure, the most commonly reported adverse experiences are diarrhea, nausea, fatigue, thrombocytopenia, hyperglycaemia, vomiting, anorexia, anaemia, neutropenia, constipation, blood creatinine increased, leukopenia, dyspnea, weight decreased, decreased appetite, alopecia, aspartate aminotransferase increased and cough are the most common adverse events.

4.1.2 Preclinical and Clinical Trial Data

Refer to the Investigator's Brochure for Preclinical and Clinical data.

4.2 Rationale

4.2.1 Rationale for the Trial and Selected Subject Population

Glioblastoma (GBM) remains one of the most fatal tumors with a median survival of about 15 months, despite aggressive combination therapy with radiation and temozolomide (TMZ). Concurrent radiotherapy (60 Gy in 30 daily fractions) with TMZ (75 mg/m²/day) followed by 6 cycles of TMZ (150–200 mg/m²/day for 5 days every 28 days) and NovoTTF are the only treatments which have shown survival benefit in newly diagnosed GBM patients [22; 24]. Thus, GBM remains a largely unmet medical need requiring novel and effective treatment strategies.

Rational for combining pembrolizumab with radiotherapy and TMZ

Part of the challenge in treating GBM is the naturally immunoprivileged environment of the brain. Pre-clinical studies have shown a significant increase in expression of PD-1 on peripheral blood CD4+ and CD8+ T cells in patients with high grade gliomas. In a study by Wei et al., PD-1+CD4+ T cells were clearly increased in peripheral blood of patients with GBM (16.3 ± 0.6 %) compared to healthy cohort (2.5 ± 0.2 %) [25]. Expression of PD-1 and PD-L1 is found in the microenvironment of most high grade gliomas [26; 27]. PD-1 is expressed on tumor-infiltrating lymphocytes whereas PD-L1 is expressed on tumor cells and microglia in GBM specimens [28].

Moreover, there is emerging evidence that radiotherapy synergizes with CTLA-4 and anti-PD 1/PD-L1 blockade and produces tumor regression and long-term survival in a variety of cancer models [29; 30; 31; 32]. In a study by Zeng et al., combination of anti-PD-1 antibody with radiotherapy in a mouse orthotopic GBM model generated robust and durable responses and doubled the survival when compared with either modality alone [33]. In this study, analysis of the brain and spinal cord of animals treated with combination therapy showed an

increase in the cytotoxic to regulatory T cell ratio with increased tumor infiltration by cytotoxic T cells (CD8+/interferon- γ +/tumor necrosis factor- α +).

Our investigator initiated trial sponsored by Merck (NCT02313272) has shown promising results in patients with recurrent GBM who are treated with hypofractionated stereotactic radiotherapy combined with pembrolizumab and bevacizumab. We have treated 32 patients so far and combination is very well tolerated and several patients have achieved objective response (complete response+ partial response). Durable responses as long as 16 months have been observed.

This supports addition of pembrolizumab to standard concurrent chemoradiotherapy for newly diagnosed GBM.

Rational for combining vorinostat and pembrolizumab with radiotherapy and TMZ

Vorinostat, an orally bioavailable hydroxymate pan-histone deacetylase (HDAC) inhibitor, has shown anti-tumor activity against GBM cell lines in vitro and in vivo orthotopic xenografts models [33]. Combination of vorinostat with TMZ and radiotherapy has resulted on synergistic effect on growth inhibition of glioma cell lines. Moreover, vorinostat readily penetrates the blood-brain barrier and has radiosensitizing properties. Tumor samples of patients with GBM who have received vorinostat before surgery has shown that vorinostat can penetrate tumors and inhibit histone acetylation [34].

A growing body of evidence indicates that epigenetic silencing of genes involved in antigen processing and immune recognition results in immune escape and resistance to immunotherapy [35; 36]. Pre-clinical experiments have shown that use of HDAC inhibitors such as vorinostat can restore tumor immune recognition and synergize with anti-PD 1/PD-L1 antibodies [36]. Studies on several murine models have shown that combination therapy significantly enhances the response to PD-1 blockade immunotherapy by robustly inducing expression of multiple chemokines in tumor cells, tumor infiltrating macrophages and T cells. In addition, this combination has resulted in augmented T cell infiltration and T-cell dependent tumor regression [37]. These results suggest that combination of HDAC inhibitors with PD-1 blockade represents a potential therapeutic strategy to maximize the immune response to checkpoint inhibitors.

Furthermore, Galanis et al. have investigated the safety and efficacy of concurrent chemoradiotherapy with TMZ and vorinostat in patients with newly diagnosed GBM. The combination therapy was safe and well tolerated without any cases of radiation necrosis. Based on this study, maximum tolerated dose (MTD) for vorinostat in combination with TMZ and radiotherapy in patients with newly diagnosed GBM is 300 mg/day, days 1-5 weekly during concurrent therapy and 400 mg/day on days 1-7 and 15-21 during maintenance therapy with TMZ [34; 38].

Collectively, we haves strong pre-clinical evidence that combining PD-1/PDL-1 blockade with HDAC inhibitors such as vorinostat and radiotherapy plus TMZ independently enhance anti-tumor immune responses and tumor regression. Hence, it is of great interest to study the

combination of all these treatment modalities in newly diagnosed GBM patients with very limited treatment options.

4.2.2 Rationale for Dose Selection/Regimen/Modification of Pembrolizumab (MK-3475)

An open-label Phase I trial (Protocol 001) is being conducted to evaluate the safety and clinical activity of single agent pembrolizumab. The dose escalation portion of this trial evaluated three dose levels, 1 mg/kg, 3 mg/kg, and 10 mg/kg, administered every 2 weeks (Q2W) in subjects with advanced solid tumors. All three dose levels were well tolerated and no dose-limiting toxicities were observed. This first in human study of MK-3475 showed evidence of target engagement and objective evidence of tumor size reduction at all dose levels (1 mg/kg, 3 mg/kg and 10 mg/kg Q2W). No MTD has been identified to date. 10.0 mg/kg Q2W, the highest dose tested in PN001, will be the dose and schedule utilized in Cohorts A, B, C and D of this protocol to test for initial tumor activity. Recent data from other clinical studies within the MK-3475 program has shown that a lower dose of MK-3475 and a less frequent schedule may be sufficient for target engagement and clinical activity.

PK data analysis of MK-3475 administered Q2W and Q3W showed slow systemic clearance, limited volume of distribution, and a long half-life (refer to IB). Pharmacodynamic data (IL-2 release assay) suggested that peripheral target engagement is durable (>21 days). This early PK and pharmacodynamic data provides scientific rationale for testing a Q2W and Q3W dosing schedule.

A population pharmacokinetic analysis has been performed using serum concentration time data from 476 patients. Within the resulting population PK model, clearance and volume parameters of MK-3475 were found to be dependent on body weight. The relationship between clearance and body weight, with an allometric exponent of 0.59, is within the range observed for other antibodies and would support both body weight normalized dosing or a fixed dose across all body weights. MK-3475 has been found to have a wide therapeutic range based on the melanoma indication. The differences in exposure for a 200 mg fixed dose regimen relative to a 2 mg/kg Q3W body weight based regimen are anticipated to remain well within the established exposure margins of 0.5 – 5.0 for MK-3475 in the melanoma indication. The exposure margins are based on the notion of similar efficacy and safety in melanoma at 10 mg/kg Q3W vs. the proposed dose regimen of 2 mg/kg Q3W (i.e. 5-fold higher dose and exposure). The population PK evaluation revealed that there was no significant impact of tumor burden on exposure. In addition, exposure was similar between the NSCLC and melanoma indications. Therefore, there are no anticipated changes in exposure between different indication settings.

The rationale for further exploration of 2 mg/kg and comparable doses of pembrolizumab in solid tumors is based on: 1) similar efficacy and safety of pembrolizumab when dosed at either 2 mg/kg or 10 mg/kg Q3W in melanoma patients, 2) the flat exposure-response relationships of pembrolizumab for both efficacy and safety in the dose ranges of 2 mg/kg Q3W to 10 mg/kg Q3W, 3) the lack of effect of tumor burden or indication on distribution behavior of pembrolizumab (as assessed by the population PK model) and 4) the assumption

that the dynamics of pembrolizumab target engagement will not vary meaningfully with tumor type.

The choice of the 200 mg Q3W as an appropriate dose for the switch to fixed dosing is based on simulations performed using the population PK model of pembrolizumab showing that the fixed dose of 200 mg every 3 weeks will provide exposures that 1) are optimally consistent with those obtained with the 2 mg/kg dose every 3 weeks, 2) will maintain individual patient exposures in the exposure range established in melanoma as associated with maximal efficacy response and 3) will maintain individual patients exposure in the exposure range established in melanoma that are well tolerated and safe.

A fixed dose regimen will simplify the dosing regimen to be more convenient for physicians and to reduce potential for dosing errors. A fixed dosing scheme will also reduce complexity in the logistical chain at treatment facilities and reduce wastage.

4.2.3 Biomarker Research

Archival tissue will be collected and assessed for direct evaluation of the intratumoral immune compartment. If biopsy or surgical tumor specimens become available following study treatment, these tissues will be included in the analysis.

5.0 METHODOLOGY

5.1 Entry Criteria

5.1.1 Diagnosis/Condition for Entry into the Trial

Newly diagnosed glioblastoma or gliosarcoma

5.1.2 Subject Inclusion Criteria

In order to be eligible for participation in this trial, the subject must:

- 1. Histologically confirmed diagnosis of World Health Organization Grade IV malignant glioma.
- 2. An interval of ≥ 21 days since surgical resection prior to treatment on the trial
- 3. Be \geq 18 years of age on day of signing informed consent.
- 4. Karnofsky performance status of 70 or higher
- 5. Demonstrate adequate organ function as defined in Table 1, all screening labs should be performed within 21 days of treatment initiation.

Table 1 Adequate Organ Function Laboratory Values

System	Laboratory Value	
Hematological		
Absolute neutrophil count (ANC)	≥1,500 /mcL	
Platelets	≥100,000 / mcL	
Hemoglobin	≥9 g/dL or ≥5.6 mmol/L without transfusion or EPO dependency (within 7 days of assessment)	
Renal		
Serum creatinine OR Measured or calculated ^a creatinine	≤1.5 X upper limit of normal (ULN) OR	
clearance	\geq 60 mL/min for subject with creatinine levels \geq 1.5 X	
(GFR can also be used in place of creatinine or CrCl)	institutional ULN	
Hepatic		
Serum total bilirubin	≤ 1.5 X ULN OR	
	Direct bilirubin ≤ ULN for subjects with total bilirubin levels > 1.5 ULN	
AST (SGOT) and ALT (SGPT)	≤ 2.5 X ULN OR ≤ 5 X ULN for subjects with liver metastases	
Albumin	≥2.5 mg/dL	
Coagulation	·	
International Normalized Ratio (INR) or Prothrombin Time (PT)	≤1.5 X ULN unless subject is receiving anticoagulant therapy as long as PT or PTT is within therapeutic range of intended use of anticoagulants	
Activated Partial Thromboplastin Time (aPTT)	≤1.5 X ULN unless subject is receiving anticoagulant therapy as long as PT or PTT is within therapeutic range of intended use of anticoagulants	
^a Creatinine clearance should be calculated	per institutional standard.	

- 6. Resting baseline O2 saturation by pulse oximetry of \geq 92% at rest.
- 7. Be willing and able to provide written informed consent/assent for the trial.
- 8. Life expectancy \geq 12 weeks
- 9. Willingness to discontinue medications known to be associated with risk of Torsades de Pointes such as quinidine, procainamide, disopyramide, amiodarone, erythromycin, clarithromycin, chlorpromazine and haloperidol.
- 10. Single lesion < 4 cm in longest diameter (diameter of enhancing lesion)
- 11. Patient shouldn't have received any anti-cancer therapy for glioblastoma in past.
- 12. Female subject of childbearing potential should have a negative urine or serum pregnancy prior to receiving the first dose of study medication. If the urine test is positive or cannot be confirmed as negative, a serum pregnancy test will be required.
- 13. Female subjects of childbearing potential (Section 5.7.2) must be willing to use an adequate method of contraception as outlined in Section 5.7.2 Contraception, for the course of the study through 120 days after the last dose of study medication.

Note: Abstinence is acceptable if this is the usual lifestyle and preferred contraception for the subject.

14. Male subjects of childbearing potential (Section 5.7.1) must agree to use an adequate method of contraception as outlined in Section 5.7.1- Contraception, starting with the first dose of study therapy through 120 days after the last dose of study therapy.

Note: Abstinence is acceptable if this is the usual lifestyle and preferred contraception for the subject.

15. Use of Optune device is allowed.

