5.3.3 Timing of Dose Administration

Trial treatment should be administered after all procedures/assessments have been completed as detailed on the Trial Flow Chart (Section 6.0). Trial treatment may be administered up to 3 days before or after the scheduled day due to administrative reasons.

All trial treatments will be administered on an outpatient basis.

Pembrolizumab will be administered as a 30 minute IV infusion every 3 weeks (+/- 3 days). However, given the variability of infusion pumps, a window of -5 minutes and +10 minutes is permitted (i.e., infusion time is 30 minutes: -5 min/+10 min).

The Pharmacy Manual contains specific instructions for the preparation of the pembrolizumab infusion fluid and administration of infusion solution.

Vorinostat should be taken with food, at regular intervals regardless of pembrolizumab infusion time. On days the patient receives pembrolizumab, the vorinostat should be taken prior to the pembrolizumab infusion.

Temozolomide should be given on empty stomach, at regular intervals regardless of pembrolizumab infusions or vorinostat. On days the patient receives pembrolizumab, the temozolomide can be taken prior to or after the pembrolizumab infusion. In patients who do not experience nausea, temozolomide can be taken after a small meal.

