5.7.2 Contraception

Pembrolizumab, vorinostat, and temozolomide may have adverse effects on a fetus in utero. Furthermore, it is not known if pembrolizumab, temozolomide and vorinostat have transient adverse effects on the composition of sperm.

For this trial, male subjects will be considered to be of non-reproductive potential if they have azoospermia (whether due to having had a vasectomy or due to an underlying medical condition).

Female subjects will be considered of non-reproductive potential if they are either:

(1) postmenopausal (defined as at least 12 months with no menses without an alternative medical cause; in women < 45 years of age a high follicle stimulating hormone (FSH) level in the postmenopausal range may be used to confirm a post-menopausal state in women not using hormonal contraception or hormonal replacement therapy. In the absence of 12 months of amenorrhea, a single FSH measurement is insufficient.);

OR

(2) have had a hysterectomy and/or bilateral oophorectomy, bilateral salpingectomy or bilateral tubal ligation/occlusion, at least 6 weeks prior to screening;

OR

(3) has a congenital or acquired condition that prevents childbearing.

Female and male subjects of reproductive potential must agree to avoid becoming pregnant or impregnating a partner, respectively, while receiving study drug and for 120 days after the last dose of study drug by complying with one of the following:

(1) practice abstinence[†] from heterosexual activity;

OR

(2) use (or have their partner use) acceptable contraception during heterosexual activity.

Acceptable methods of contraception are[‡]:

Single method (one of the following is acceptable):

- intrauterine device (IUD)
- vasectomy of a female subject's male partner
- contraceptive rod implanted into the skin

Combination method (requires use of two of the following):

- diaphragm with spermicide (cannot be used in conjunction with cervical cap/spermicide)
- cervical cap with spermicide (nulliparous women only)
- contraceptive sponge (nulliparous women only)
- male condom or female condom (cannot be used together)
- hormonal contraceptive: oral contraceptive pill (estrogen/progestin pill or progestinonly pill), contraceptive skin patch, vaginal contraceptive ring, or subcutaneous contraceptive injection

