†Abstinence (relative to heterosexual activity) can be used as the sole method of contraception if it is consistently employed as the subject's preferred and usual lifestyle and if considered acceptable by local regulatory agencies and ERCs/IRBs. Periodic abstinence (e.g., calendar, ovulation, sympto-thermal, post-ovulation methods, etc.) and withdrawal are not acceptable methods of contraception.

‡If a contraceptive method listed above is restricted by local regulations/guidelines, then it does not qualify as an acceptable method of contraception for subjects participating at sites in this country/region.

Subjects should be informed that taking the study medication may involve unknown risks to the fetus (unborn baby) if pregnancy were to occur during the study. In order to participate in the study subjects of childbearing potential must adhere to the contraception requirement (described above) from the day of study medication initiation (or 14 days prior to the initiation of study medication for oral contraception) throughout the study period up to 120 days after the last dose of trial therapy. If there is any question that a subject of childbearing potential will not reliably comply with the requirements for contraception, that subject should not be entered into the study.

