6.0 TRIAL FLOW CHART

6.1 Study Flow Chart

Concurrent Radiotherapy Phase

Trial Period:	Screeni	ng Phase						Tr	eatmen	t Cycle	es			
Treatment Cycle/Title:	Pre- screening (Visit 1)	Main Study Screening (Visit 2) ^a	Cycle 1 (Concurrent therapy with radiation, 12 weeks)											
Scheduling Window (Days):		-21 to -1	D1 ± 3	D8 ± 3	D15 ± 3	D22 ± 3	D29 ± 3	D36 ± 3	D43 ± 3	D50 ± 3	D57 ± 3	D64 ± 3	D71 ± 7	D78 ± 3
Administrative Procedures									ı					
Informed Consent	X													
Inclusion/Exclusion Criteria		X												
Demographics and Medical History	X	X	X			X			X			X		
Prior and Concomitant Medication Review	X	X	X			X			X			X		
Radiation therapy				(Total c	lose of (X 60 Gy; 1	Monday	-Friday	·)					
Temozolomide					F	X Every da	ıy						X (5 day regimen every 28 days)	
Pembrolizumab			X			X			X			X		
Vorinostat				l	Dail	y one v	-		-	ek duri starting	-		+/- 3 days	
Post-study anticancer therapy status														
Survival Status														
Clinical Procedures/Assessments														
Review Adverse Events ^c			X			X			X			X		
Full Physical Examination	X	X	X			X			X			X		

Trial Period:	Screeni	Treatment Cycles												
Treatment Cycle/Title:	Pre- screening (Visit 1)	Main Study Screening (Visit 2) a	Cycle 1 (Concurrent therapy with radiation, 12 weeks)											
Scheduling Window (Days):		-21 to -1	D1 ± 3	D8 ± 3	D15 ± 3	D22 ± 3	D29 ± 3	D36 ± 3	D43 ± 3	D50 ± 3	D57 ± 3	D64 ± 3	D71 ± 7	D78 ± 3
Vital Signs and Weight	X	X	X			X			X			X		
EORTC QLQ-C30 and BNS20 Questionnaire			X			X			X			X		
Karnofsky Performance Status	X	X	X			X			X			X		
Laboratory Procedures/Assessments: analy	sis perform	ed by LOCA	L labor	ratory										
Pregnancy Test – Urine or Serum β-HCG		X												
PT/INR and aPTT		X												
CBC with Differential	X	X	X	X	X	X	X	X	X	X	X	X	X	X
Comprehensive Serum Chemistry Panel	X	X	X			X			X			X		
Urinalysis	X	X	X			X			X			X	X	
T3, FT4 and TSH	X	X	X			X			X			X		
Efficacy Measurements														
Brain MRI with/without contrast		X											X	
Tumor Biopsies/Archival Tissue Collection	/Correlative	e Studies Bloo	od											
Archival or Newly Obtained Tissue Collection		X												
Correlative Studies Blood Collection			X			X			X					

^a Visit 1 assessment (physical examination and laboratories) can be used for main study screening (visit 2) if visit 2 occurs within 3 days from visit 1.

^b There will be two follow up visits which include full physical examination, laboratories, and brain MRI.

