7.1.3 Laboratory Procedures/Assessments

Laboratory tests for hematology, chemistry, urinalysis, and others are specified in Table 6. The total amount of blood to be drawn over the course of the trial (from pre-trial to post-trial visits), including approximate blood volumes drawn by visit and by sample type per subject can be found in the Procedures Manual.

Table 6 Laboratory Tests

Hematology	Chemistry	Urinalysis	Other
Hematocrit	Albumin	Blood	Serum β-human chorionic gonadotropin†
Hemoglobin	Alkaline phosphatase	Glucose	(β-hCG)†
Platelet count	Alanine aminotransferase (ALT)	Protein	Thyroid stimulating hormone (TSH)
WBC (total and differential)	Aspartate aminotransferase (AST)	Urine pregnancy test †	Total thriiodothyronine (T3)
Red Blood Cell Count	Lactate dehydrogenase (LDH)	Microscopic exam (If abnormal)	Free tyroxine (T4)
Absolute Neutrophil Count	Uric Acid	results are noted	
Absolute Lymphocyte Count	Calcium		
	Chloride		
	Glucose		
	Phosphorus		Blood for correlative studies
	Potassium		
	Sodium		
	Magnesium		
	Total Bilirubin		
	Direct Bilirubin (If total bilirubin is elevated above the upper limit of normal)		

[†] Perform on women of childbearing potential only. If urine pregnancy results cannot be confirmed as negative, a serum pregnancy test will be required.

[‡] If considered standard of care in your region.

After Cycle 1, pre-dose laboratory procedures can be conducted up to 72 hours prior to dosing. Results must be reviewed by the investigator or qualified designee and found to be acceptable prior to each dose of trial treatment.

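### The only test marked in the pregnancy-test row can be 21 days old at first dose, so a pregnancy barred by exclusion 18 can go undetected on Day 1, and Table 6 disagrees on repeat testing

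*Combined protocol and SAP*

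**What the plan says.** **Test timing.** Under inclusion 12 in section 5.1.2, a woman of childbearing potential "should have a negative urine or serum pregnancy prior to receiving the first dose of study medication" test; no number of hours or days is attached. Inclusion 5 in the same section adds that "all screening labs should be performed within 21 days of treatment initiation". In the section 6.1 flow chart, the row "Pregnancy Test – Urine or Serum β-HCG" carries one mark, under main study screening (Visit 2, Day -21 to -1). The row is empty on Cycle 1 Day 1 and at every later Cycle 1 visit. It is printed again, still empty, for Cycles 2 to 5, end of treatment and follow-up.

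**Table 6 (section 7.1.3).** A urine pregnancy test is listed in the urinalysis column, for women of childbearing potential only. Urinalysis is marked on Cycle 1 Day 1 and at later visits.

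**Contraception.** Section 5.7.2 gives two wordings: "while receiving study drug and for 120 days after the last dose of study drug", and, on the start, "from the day of study medication initiation (or 14 days prior to the initiation of study medication for oral contraception". Inclusion 13 (women) says "for the course of the study through 120 days after the last dose of study medication" and names no start day.

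**Pregnancy as an exclusion.** Exclusion 18 (section 5.1.3) bars a woman who is pregnant or plans to become so, with a period that begins at pre-screening or screening.

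**The concern.** Cycle 1 Day 1 starts radiotherapy, temozolomide, vorinostat and pembrolizumab together, and section 5.7.2 warns that each of the three drugs could harm a fetus. A test done at the start of the screening window can miss a pregnancy in two ways: it may be too early to show, or conception may follow the test. Exclusion 18 forbids treating such a woman, but an exclusion works only if some procedure can find the condition, and the dedicated row provides none between screening and first dose.

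The same gap continues on treatment. Section 5.8 discontinues a subject with a confirmed positive serum pregnancy test, yet the dedicated row schedules no test after screening that could trigger this, and section 7.2.2 relies on pregnancies that subjects report themselves. Because Table 6 points the other way, two careful sites could run different schedules, each with textual support.

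**Working it through.** No sample-size or power figure is involved. The check is a count of days and a comparison of passages.

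**1. Age of the test at first dose**

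| Input | Value | Source |
|---|---|---|
| Window for the marked test | Day -21 to -1 | Section 6.1 flow chart, Visit 2 |
| Limit on screening laboratory work | 21 days before treatment | Inclusion 5 |
| Dosing window | ±3 days | Section 5.3.3 |
| Limit in inclusion 12 | none | Section 5.1.2 |

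- Maximum, with no Day 0: Day -21 to -1 is 20 days, plus 1 day to Day 1, giving 21 days. Counting a Day 0 gives 22.
- Section 5.3.3 allows that "Trial treatment may be administered up to 3 days before or after the scheduled day due to administrative reasons". Added to the screening window this would give 21 + 3 = 24 days, but inclusion 5 caps screening laboratory work at 21. Section 7.1.5.1.1 also asks for treatment within 21 days of consent.
- Minimum: Day -1 to Day 1 is 1 day.

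The result is therefore 1 to 21 days old.

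**2. Is the test repeated?**

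| Source | Day 1 | Later visits |
|---|---|---|
| Pregnancy-test row, section 6.1 | not marked | not marked |
| Table 6 with the urinalysis row | implied | implied wherever urinalysis is marked |

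In Cycle 1, blood count, chemistry, urinalysis and thyroid tests are marked at both screening and Day 1. The empty Day 1 cell in the pregnancy row is thus more naturally read as intended than as an extraction fault. Section 5.3.3 has treatment follow completion of the flow-chart procedures. A site working from the dedicated row has no pregnancy test to complete on Day 1.

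**3. Contraception between test and first dose, under the explicit start in section 5.7.2**

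- Methods other than oral contraception: the duty starts on Day 1, leaving up to 21 days after the test with no stated duty.
- Oral contraception: the duty starts 14 days earlier, leaving up to 21 - 14 = 7 days.
- Exclusion 18 already applies throughout this interval, but it concerns pregnancy and the intention to conceive. It does not state a contraceptive duty.

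The two periods start at different points, and inclusion 13 does not say which is meant.

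**The case against.** Much of the opposing case is sound and limits what can be claimed.

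- A reader might infer that a woman could be pregnant on Day 1 with every criterion met. The documents do not support that: she fails exclusion 18. The gap is in detection.
- A reader might infer that women need no contraception for three weeks before treatment. That is the worst case under one sentence of section 5.7.2. Oral contraception has a 14-day lead-in, inclusion 13 can be read as covering the whole study, and section 5.7.2 keeps out anyone whose compliance is in doubt. The wording that ties contraception to the first dose within the eligibility criteria is in inclusion 14, which is for men.
- If Table 6 governs, a Day 1 test is already required and the timing problem disappears. This cannot be ruled out. The dedicated row is the more natural guide, but the conflict is itself a defect.
- The sentence "After Cycle 1, pre-dose laboratory procedures can be conducted up to 72 hours prior to dosing" might be taken as a standard that the pregnancy test breaches. It covers pre-dose work after Cycle 1 and is not an eligibility window. Inclusion 5 gives this test the same 21 days as the other screening laboratory work.
- Twenty-one days is a maximum, and inclusion 12 does not stop a site from repeating the test.
- Replacing the screening test with a Day 1 test would be a mistake. Under section 5.4 the sponsor reviews eligibility and assigns the dose level after baseline assessments, and needs a result by then.

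What remains is that no limit is stated in inclusion 12, the dedicated row allows a three-week-old result, and Table 6 and the contraception passages do not match it.

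**Conclusion.** The point holds as a detection gap with inconsistent wording. Following the flow chart's own pregnancy-test row, the result relied on at first dose may be 1 to 21 days old, and that row schedules no further test in any of the five cycles. Table 6 implies the opposite. The contraception start in section 5.7.2 falls up to 21 days after the test (up to 7 for oral contraception), whereas exclusion 18 runs from pre-screening or screening.

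This rests on two readings: that the dedicated row takes precedence over the urinalysis column of Table 6, and that the 21-day limit in inclusion 5 covers the pregnancy test. The documents do not say how many of the planned maximum of 32 patients will be women of childbearing potential, so the number affected cannot be estimated and may be small. The change is still worth making, because the possible harm is serious and the correction is minor.

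**What to change.** 1. Keep the screening test, so that a result is available for enrolment approval under section 5.4.
2. Add a mark in the pregnancy-test row at Cycle 1 Day 1, before the first dose, for women of childbearing potential. Urine is already collected that day.
3. Reword inclusion 12 to name both time points. Because pembrolizumab may start up to 3 days either side of the first radiotherapy day (section 5.3), the wording should make clear that the test precedes whichever study treatment is given first.
4. Make the pregnancy-test row and Table 6 agree on Day 1 and on every later visit, so that sites know whether on-treatment testing is intended.
5. Reconcile the contraception start in inclusion 13 and section 5.7.2 with the period in exclusion 18. Which rule is right is for the sponsor to decide.

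The cost is protocol and flow-chart wording plus one inexpensive urine test per woman concerned, with no added visit or sample. The downside is that a positive result could appear on the planned start day.
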